#### Exposure:

Exposure to study drug will be summarized descriptively using safety population in PPD as :

- number of applications made
- total amount of gel used.

Study drug exposure will also be listed using safety population along with the drug compliance in the **PPD**.

#### 4.4.2 Prior and Concomitant Medication/Non-Drug Therapies or Procedures

Prior medications (stopped prior to day 1) will be listed by subject, with preferred term, indication, dose, dose form, frequency, route, start date and start and end day (PPD

Prior medications will be summerized using ITT population in PPD

Concomitant medications (ongoing at Day 1 or started on or after Day 1) will be listed similarly, with the addition of a flag for forbidden concomitant therapies (**PPD**).

).

Tables and listings described in this section will be presented for the ITT population. The medication listing will include the preferred term, indication, single dose, frequency, route, start

GlaxoSmithKline Consumer Healthcare Confidential

Page 17 of 36

211206

Statistical Reporting and Analysis plan Draft V2.0 20JAN2021

date, and end date or ongoing at final visit (when appropriate) and a flag whether the medication was Prior or Concomitant (**PPD**).

Concomitant medications (ongoing at randomization or started after randomization) will be summarized by treatment, anatomical area and therapeutic use or preferred term, and the number and percentage of subjects who took any concomitant medication will be presented (PPD) using ITT population.

The number and percent of subjects taking disallowed concomitant medications will be summarized similarly (**PPD**).

All the information related to concomitant medication will be obtained from Current/Prior/Concomitant Medication CRF page.

Non-drug therapies/procedures will be listed using ITT population (**PPD**). Information related to non-drug procedures/therapies will be taken from Non-Drug Treatments/Procedures CRF Page.

#### 4.4.3 Rescue Medication

The investigator will provide rescue medication (paracetamol 500mg tablets) to the subjects at the baseline visit. Rescue medication will be re-dispensed on Day 5 i.e.at Visit 3. Subjects are not allowed to take rescue medication within 6 hours of study visits and within 12hours of Day 5. Following information will be documented in the Rescue Medication CRF page –

- Rescue medication taken (yes/no) (RMYN)
- Pain intensity (RMPI) and pain relief (RMPR) before taking rescue medication
- Reason for use of rescue medication (RMREAS)
- Time (RMSTTM) and date (RMSTDTC) of rescue medication
- Number of tablets taken (RMNUM)

Summuary of all the above mentioned points will be displayed in PPD . and will be listed in PPD .

Time to first use of rescue medication will be analyzed using the survival estimate of median time to event for each treatment group along with the CI for median. P-value from Log Rank test will be used to compare the median times between the treatment groups (**PPD**).

Kaplan Meier plot will be presented for the survival probabilities against the time points for both the treatment groups (In case number of events are considerable).

Subjects with no use of rescue medication will be censored at their last available date in the study.

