6.10 Rescue Medication

The investigator will provide rescue medication (paracetamol, 500 mg tablets) to the subject at the baseline visit. Rescue medication will be re-dispensed on Day 5 (V3), if necessary.

Subjects will be instructed to take only the rescue medication provided for pain in the ankle or any other pain (e.g., headache) or fever (e.g., due to common cold) they might experience during the trial. One tablet may be taken, repeated after at least 4 hours, if needed, up to a maximum of 2000 mg (four tablets) per day. No rescue medication is allowed within 6 hours prior to the study visits or within 12 hours of Study Visit 3.

The subject will receive a Subject Diary at Visit 1, Visit 2, and Visit 3 to record the information described in Section 6.8. At each visit, the investigator or designee will review the rescue medication use recorded in the diary and will transfer the relevant information to the CRF. Empty packages and rescue medication not used will be returned to the investigator. The investigator or designee will then compare the packages vs. the subject's rescue medication form and any discrepancies will be noted in the CRF.

The investigator will further investigate any instances in which rescue medication was taken for reasons other than ankle sprain and complete the Adverse Event Form, if appropriate.

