12.2.6 Secondary Analysis(es)

Secondary outcome measures (endpoints) include:

- Change from baseline of POM on VAS on Days 3 and 8 respectively
- Tenderness measured by pressure algometry on Days 3, 5 and 8 (change from baseline and difference between the measurement in injured area and contralateral area)
- Change from baseline Ankle Joint Function (Karlsson Scoring Scale) on Days 3, 5 and 8
- Circumference measurement of swelling (change from baseline in circumference of affected ankle and comparison to non- affected ankle by Figure of Eight method on Days 3, 5 and 8)
- Pain Intensity and Pain Relief
 - Sum of Pain Intensity Difference (SPID) From hours 0 24 post first dose (corresponding to Day 1) and from hours 96 120 post first dose (corresponding to Day 5)
 - Total Pain Relief (TOTPAR) From hours 0 24 post first dose (corresponding to Day 1) and from hours 96 120 post first dose (corresponding to Day 5)

TOTPAR and SPID will be calculated as weighted sums of the Pain Relief Score and Pain Intensity Difference at each timepoint respectively:

 $TOTPAR = \Sigma R_t^x (time_t - time_{t-1})$

Where R_t = the pain relief score at time t and time t = time in hours post first dose

 $SPID_t = \Sigma PID_t (time_t - time_{t-1})(h)$

Where PI is pain intensity

- Use of rescue medication, for ankle sprain and overall
 - Total number of tablets used
 - Total number of days on which rescue medication was used

Figures will show the time course of outcomes by treatment group for key quantitative outcomes.

For POM, Karlsson score, tenderness, swelling and diary assessments (SPID and TOTPAR), an ANCOVA model including treatment group and center as main effects, and the baseline value as covariate (those outcomes for which there is a baseline) will be used for analysis, with the treatment difference and 95% confidence interval (two-sided) presented for each assessment.

Use of rescue medication (number of tablets and days used) will be compared between treatments using the CHM method (modridit scores) stratified by center, with the median treatment differences and 95% confidence intervals (2-sided) presented using Hodges-Lehmann estimation.

These secondary endpoints will be analyzed using the per protocol and mITT populations.

GlaxoSmithKline Consumer Healthcare Confidential Template Version Effective: 18-May-18 (CCR #11475) Page **54** of **64**

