#### **Censoring Rule:**

GlaxoSmithKline Consumer Healthcare Confidential

Page 18 of 36

Event : If event occurred then value of censor is 0, time will be derived as follows: Date of First Occurrence of Event- Date of Randomization + 1

Censor: If event not occurred then value of censor is 1, time will be derived as follows: Last Available Date in the study - Date of Randomization + 1

Where, Last Available Date in the study = Maximum of (Date of Discontinuation, Date of Death, Date of Follow-up, Study Completion Date)

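### SAP Section 4.4.3 compares the arms only on first rescue use for any reason, so the ankle-pain version of the rescue endpoints has no between-arm comparison

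*SAP*

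**What the plan says.** Protocol Section 6.10 makes the supplied paracetamol the only remedy subjects are told to use "for pain in the ankle or any other pain (e.g., headache) or fever". Rescue data will therefore mix ankle and non-ankle use. The protocol allows for this. Its objectives table defines both rescue endpoints (number of tablets, number of days with use) for ankle pain and overall. Section 12.2.6 repeats the split, "Use of rescue medication, for ankle sprain and overall", and compares the arms by a center-stratified modridit test with Hodges-Lehmann estimates and intervals. SAP Table 1-2 keeps the same split endpoints.

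SAP Section 4.4.3 then specifies a different analysis: "Time to first use of rescue medication will be analyzed using the survival estimate of median time to event for each treatment group", with "P-value from Log Rank test will be used to compare the median times between the treatment groups" and, if events suffice, a Kaplan-Meier plot. On censoring it says "Subjects with no use of rescue medication will be censored at their last available date in the study". The censoring rule sets the event time as "Date of First Occurrence of Event- Date of Randomization + 1" and does not define the event by reason. The reason for use (RMREAS) is on the CRF, and Section 4.4.3 sends it to a summary and a listing.

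SAP Section 5 states that rescue is now analysed as time to event and that the planned Hodges-Lehmann analysis is not done. The rationale in its Table 3 does not mention reason for use. The modridit test appears nowhere in the SAP, and the secondary efficacy lists in Sections 4.5.2 and 4.6.1 omit rescue.

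**The concern.** Rescue taken for the ankle is the version that speaks to inadequate analgesia from the gel. Under the SAP rule as written, a subject who takes one tablet for fever on Day 2 and none for the ankle is an event at Day 2. A subject with a headache tablet on Day 2 and a first ankle tablet on Day 4 is also an event at Day 2, and the ankle use never enters the comparison.

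Two things follow. A secondary endpoint stated in both documents ends up with no test, estimate or interval between arms. And the comparison that remains adds events that the gel would not be expected to influence, which makes it less able to show a difference in ankle-pain rescue if there is one.

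**Working it through.** **Endpoint against analysis**

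| Endpoint in protocol and SAP Table 1-2 | Between-arm analysis in protocol 12.2.6 | Between-arm analysis in SAP |
|---|---|---|
| Tablets, ankle pain | modridit test, Hodges-Lehmann | none |
| Tablets, overall | modridit test, Hodges-Lehmann | none |
| Days, ankle pain | modridit test, Hodges-Lehmann | none |
| Days, overall | modridit test, Hodges-Lehmann | none |
| Time to first use, any reason | not planned | medians, log-rank p-value |
| Time to first use, ankle pain | not planned | none |

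**No design figure to reproduce for rescue.** The only sample-size calculation is for the primary endpoint. It reproduces: 2 × 22² × (1.96 + 0.8416)² / (13 − 5)² = 118.7, so 119 per arm against the stated 120. It does not bear on this point.

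**Illustration of lost sensitivity.** From the documents: 150 randomized per arm and 7 days of treatment. Assumed, because no rescue rates are given: constant hazards, the same non-ankle hazard in both arms, ankle use by Day 7 of 10%, 20% or 40% in the DDEA 1.16% (reference) arm, non-ankle use by Day 7 of 0% to 20%, and a true ankle-use hazard ratio (HR) of 1.5 or 2.0.

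- Daily hazard: h = −ln(1 − p)/7
- Any-use HR = (HR × h_ankle + h_other)/(h_ankle + h_other)
- Events D = 150 × [1 − exp(−7 × reference hazard)] + 150 × [1 − exp(−7 × test hazard)]
- Log-rank power at two-sided 5% = Φ(√(D/4) × ln HR − 1.96)

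Worked case with 20% ankle use and HR 2.0:

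- Ankle events only: h_ankle = 0.2231/7 = 0.0319. D = 30 + 54 = 84. √(84/4) × 0.693 − 1.96 = 1.22, so power is 89%.
- With 10% non-ankle use: h_other = 0.1054/7 = 0.0151. Any-use HR = (0.0638 + 0.0151)/(0.0319 + 0.0151) = 1.68. D = 106. √(106/4) × 0.518 − 1.96 = 0.71, so power is 76%.

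All cases, as HR entering the test / power:

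| Ankle use, true HR | 0% other | 2% | 5% | 10% | 20% |
|---|---|---|---|---|---|
| 10%, 2.0 | 2.00 / 62.8% | 1.84 / 56.5% | 1.67 / 48.8% | 1.50 / 39.2% | 1.32 / 27.2% |
| 20%, 2.0 | 2.00 / 88.8% | 1.92 / 86.4% | 1.81 / 82.6% | 1.68 / 75.9% | 1.50 / 62.8% |
| 40%, 2.0 | 2.00 / 99.1% | 1.96 / 98.9% | 1.91 / 98.5% | 1.83 / 97.6% | 1.70 / 94.9% |
| 20%, 1.5 | 1.50 / 40.8% | 1.46 / 38.1% | 1.41 / 34.6% | 1.34 / 29.7% | 1.25 / 22.7% |

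The 0% column is what an ankle-pain event definition would give. The SAP does not report a hazard ratio; it is used here only to get at the power of the log-rank test, which the SAP does report. In the 20% ankle-use, HR 2.0 rows the medians add little: even with 20% non-ankle use, any use by Day 7 is 1 − 0.8 × 0.8 = 36% in the reference arm and 1 − 0.8² × 0.8 = 49% in the test arm, so neither median is reached.

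**The case against.** The strongest reply is that first use for any reason is a legitimate analysis. Every statement of the rescue endpoint asks for an overall version, and this supplies one. That stands: a reader might infer that counting headache or fever tablets contradicts the protocol, and it does not. What is missing is the ankle-pain companion.

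Second, a reader might infer that dilution makes the arms look alike and so helps a non-inferiority claim. The documents do not support that. Success rests only on Day 5 pain on movement against the 13 mm margin; the rescue comparison has no margin, no non-inferiority hypothesis and no part in the success rule.

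Third, the size could be negligible. Subjects are healthy adults followed for about a week, and those with other pain conditions can be excluded at entry. Non-ankle use may be rare, and its equality across arms is assumed. This stands too.

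Fourth, the SAP never says in words that a headache tablet counts. The rescue sample code and the display list cannot be read in the public copy, and Section 4.4.3 does promise a summary that covers reason and tablet number. So an ankle-pain output may exist. But the text that can be read has no filter on RMREAS, censors only subjects with no use at all, and attaches no test or interval to the summary. If a filter is intended, the SAP has to state it.

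Finally, any-use avoids reliance on the subject's attribution, and avoids the problem that paracetamol taken for a headache also relieves the ankle. Those are reasons to keep it beside the ankle-pain version, not instead of it.

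**Conclusion.** The concern holds as a gap in the analysis of a secondary endpoint. Followed exactly, the SAP text gives ankle-pain rescue no between-arm comparison, and the one comparison it keeps mixes in use for other reasons. The tablet and day endpoints also lose their comparisons, for ankle pain and overall alike.

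The direction of the lost sensitivity follows if non-ankle use is similar in both arms. Its size cannot be derived from the documents. With a true ankle-use hazard ratio of 2.0 and the assumptions above, the loss of log-rank power runs from under 1 percentage point (40% ankle use, 2% to 5% non-ankle use) to about 26 points (20% ankle use, 20% non-ankle use) or 36 points (10% ankle use, 20% non-ankle use). The primary conclusion on Day 5 pain on movement is not affected.

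**What to change.** In SAP Section 4.4.3:

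- Add a time-to-first-use analysis whose event is the first dose with RMREAS equal to ankle pain. State that an earlier dose for another reason is neither an event nor a censoring point. Subjects with no ankle-pain dose are censored at their last available date.
- Keep the any-use analysis and label it overall.
- Compare the arms on tablets and on days with use, each for ankle pain and overall, by the center-stratified modridit test of protocol Section 12.2.6. A time-to-event table does not address those endpoints. If any of these comparisons is to be dropped, SAP Section 5 should name it and say why.

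The change should be made before the SAP is signed and the codes are released, in the order set out in SAP Section 2.2, so that the event definition is not chosen with the results in view.

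The cost is a few sentences and a few extra tables and a plot; the reason for use is already collected. The downsides are fewer events in the ankle-pain version, reliance on the subject's stated reason, and the chance that paracetamol taken for another reason delays ankle-attributed use. Showing both versions side by side lets the reader judge the last two.

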#### 211206

Statistical Reporting and Analysis plan Draft V2.0 20JAN2021

| Object | ives   | Endpoints   |  |  |
|--------|--|---|--|--|
| •      | To assess efficacy of treatments for
swelling of affected ankle as measured
by Figure of Eight method                | Difference between circumference of affected
ankle to unaffected ankle by Figure of Eight
method on Days 3, 5 and 8 |  |  |
| •      | To assess efficacy of treatments for
effect on pain intensity as measured by
Sum of Pain Intensity Difference (SPID) | SPID from $0 - 24$ hours post first dose (Day 1) and from $0 - 24$ hours post first dose (Day 5)                          |  |  |
| •      | To assess effect of treatments for effect
on pain relief as measured by Total Pain
Relief (TOTPAR)                   | TOTPAR from 0 – 24 hours post first dose (Day 1) and from 0 – 24 hours post first dose (Day 5)                            |  |  |
| ٠      | To assess the use of rescue medication among subjects  | Number of tablets usedto treat ankle pain and overall   |  |  |
| •      | To assess the use of rescue medication among subjects  | Number of days on which rescue medication was used to treat ankle pain and overall  |  |  |
| Safety |  | · · · ·   |  |  |
| •      | To assess safety of DDEA 1.16% and DDEA 2.32% gels after 1 week of use   | Number, incidence, and severity of adverse events following dosing with study medication                                  |  |  |

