## 4.6 Analysis of Secondary Objectives

## 4.6.1 Efficacy (Secondary)

All the secondary endpoints POM at day 3 and 8, Karlsson score, tenderness, swelling and diary assessments (SPID and TOTPAR) will be analyzed using an ANCOVA model with treatment and center as fixed effect, baseline assessment for the corresponding endpoints as covariate. Treatment differences and two-sided 95% CI will be presented.

The secondary efficacy analyses will be performed and also be listed on mITT and PP population.

- Change from baseline of POM (CRF page: Pain on Movement; VAS score will be obtained from VASSCRL) on VAS on days 3 and 8 respectively (PPD).
- Tenderness measured by pressure algometry on days 3, 5 and 8 which will be analysed using change from baseline and difference between the measurement in injured area (CRF page: Tenderness; measurement for study ankle : QS\_INJA) and contralateral area (CRF page: Tenderness; measurement for study ankle : QS\_CLTA) (**PPD**)...
- Change from baseline Ankle Joint Function (Karlsson Scoring Scale; CRF page: Ankle Joint Function: Variable : Total Score KSSTS) on days 3, 5 and 8 (PPD)...
- Circumference measurement of swelling on days 3, 5 8 which will be analysed using change from baseline in circumference of affected ankle and comparison to non-affected ankle by Figure of Eight method (CRF Page:Ankle swelling; Variables: FOEMINSC and FOEMCASC respectively.) (PPD ;)..
- Pain Intensity and Pain Relief (CRF Page: Subject Diary(Day 1/5) ; variables will used to calculate the Pain Intensity and Pain Relief are DPI and DPR respectively for each timepoint (DSTMPT))
- Pain Intensity (PPD
  - Pain intensity will be analysed based on the Sum of Pain Intensity Difference (SPID). SPID is defined as from 0 -24 hours post first dose corresponding to day 1 and from 0-24 hours post first dose corresponding to day 5.
  - SPIDt=>PIDt(timet-timet-1)(h), where, PIDt=pain intensity score (DPI from CRF page corresponding to day); timet=time in hours post first dose

GlaxoSmithKline Consumer Healthcare Confidential

Page 23 of 36

211206

Statistical Reporting and Analysis plan Draft V2.0 20JAN2021

- Pain Relief (**PPD** 
  - Pain relief will be analysed based on the Total Pain Relief (TOTPAR). TOTPAR is defined as from 0-24 hours post first dose corresponding to day 1 and from 0-24 hours post first dose corresponding to day 5.

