## 5 Changes to the Protocol Defined Statistical Analysis Plan

- 1. Rescue medication analysis has been performed considering time to event data. Whereas, protocol planned "Hodge Lehmann" analysis has not been performed.
- 2. For Pain Intensity and Pain Relief, as per protocol for Day 1 it is "Sum of 0-24 hrs" and "Sum of 96-120 hrs". Based on discussion and time consideration Day 5 will also be displayed as "Sum 0-24 hours".

GlaxoSmithKline Consumer Healthcare Confidential

Page 27 of 36

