#### 211206

Statistical Reporting and Analysis plan Draft V2.0 20JAN2021

- 3. Compliance-Sensitivity analysis: Subjects with good compliance has been added in analysis to check if there is any change in variability in POM.
- 4. There will be additional sensitivity analysis conducted for COVID 19 affected subjects for which protocol will not be updated.
- 5. The definition of Per Protocol Population has been modified in the RAP.
- 6. The protocol deviation criterion of compliance has been modified.

Any changes from the originally planned statistical analysis specified in the protocol are outlined in Table 3.

 Table 3
 Changes to Protocol Defined Analysis Plan

| Protocol                                   | Reporting & Analysis Plan    |  |
|--|------------------------------|--|
| Statistical
Analysis
section         | Statistical
Analysis Plan | Rationale for Changes  |
| • Section
12,
Subsection
12.2.6   | • Section 4.4.3              | • Rescue medication can be clearly analysed defining time to event data.   |
| • Section
12,
Subsection
12.2.6   | • Section 4.5.2              | • Sine the "Day 5", 96 hour is not actual 96th hour with respect to first treatment start time, so as per clinical consideration it's start of Day 5 and consider as 0 hour of Day 5.  |
| • New addition                             | • Section 4.5.1              | • Compliance Sensitivity Analysis: This analysis has
been done to check if there is any change in variability
in POM based on good compliance  |
| • New addition                             | • Section 4.7.5              | • COVID analysis: As the pandemic started at the time of recruitment, as per regulatory requirement sensitivity analysis is planned for COVID patients, if any.  |
| • Section
12.2.
Subsection
12.2.1 | • Section 4.2.3              | • It was observed that most of the subjects has $50\% \le$ weight compliance $\le 80\%$ . However these subjects has full and proper Pain on Movement measurements available. Based on these observations it has been decided to re look on the definition of PP Population. |
| • New addition                             | • Section 4.2.2              | • For overdosed subjects the PP exclusion reason was
updated as "Other deviation-weight
compliance >=143% or application   |

GlaxoSmithKline Consumer Healthcare Confidential

Page 28 of 36

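### The SAP keeps rescue tablets and days of use as secondary endpoints but replaces their only planned between-arm comparison with time to first use, which measures neither

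*SAP*

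**What the plan says.** **Endpoints.** SAP 1.2 lists two rescue endpoints, as the protocol does. One is the number of tablets, for ankle pain and overall. The other is "Number of days on which rescue medication was used to treat ankle pain and overall".

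**Protocol analysis.** Protocol 12.2.6 states: "Use of rescue medication (number of tablets and days used) will be compared between treatments using the CHM method (modridit scores) stratified by center". We read CHM as Cochran-Mantel-Haenszel (CMH). The same sentence adds Hodges-Lehmann differences with two-sided 95% confidence intervals, and the section analyses its secondary endpoints on PP and mITT.

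**SAP analysis.** SAP 4.4.3 states: "Time to first use of rescue medication will be analyzed using the survival estimate of median time to event for each treatment group", with a log-rank p-value and a possible Kaplan-Meier plot. Its censoring rule sets the event time as "Date of First Occurrence of Event- Date of Randomization + 1". The section also promises a summary and listing of the rescue items on the CRF: whether taken, pain before the dose, reason, date, time and number of tablets.

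**Secondary efficacy sections.** SAP 4.6.1 covers "All the secondary endpoints POM at day 3 and 8, Karlsson score, tenderness, swelling and diary assessments (SPID and TOTPAR" and assigns them to ANCOVA. Neither 4.5.2 nor 4.6.1 mentions rescue use.

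**Declared change.** SAP section 5 says: "Rescue medication analysis has been performed considering time to event data", and that the Hodges-Lehmann analysis is not done. Table 3 gives the reason: "Rescue medication can be clearly analysed defining time to event data".

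**The concern.** Two listed endpoints are left with no stated between-arm estimate, interval or test, and the variable analysed in their place is not a version of either. It stops at the first tablet, it is not split by reason although both endpoints are, and it uses dates only although the clock time of each dose is collected. The stated rationale says that time to event is a clear way to analyse rescue use. It does not say why amount and duration are no longer compared while they stay on the endpoint list.

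What is at stake is interpretation. Paracetamol is allowed on top of both gels, so a reader of a non-inferiority result on Day 5 pain on movement (POM) will ask whether the arms used similar amounts of it. The protocol's comparison of tablets and days goes some way to answering that. Time to first use answers a different question.

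**Working it through.** **1. Plan's own figures.** The documents give no operating figure for the rescue analysis. The primary sample size reproduces: 2 × 22² × (1.960 + 0.842)² / (13 − 5)² = 118.7, so 119 per arm against about 120 stated. Nothing here changes it.

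**2. Count of comparisons.** Protocol 12.2.6: 2 measures (tablets, days) × 2 reasons (ankle, overall) = 4. SAP text: 0.

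**3. What the substitute records.** Protocol 6.10 allows rescue "up to a maximum of 2000 mg (four tablets) per day".
- Subject A takes 1 tablet on Day 1 and no more: 1 tablet, 1 day of use.
- Subject B takes 4 tablets a day for 7 days: 4 × 7 = 28 tablets, 7 days of use.
- SAP event time for both: Day 1 date − Day 1 date + 1 = 1, with an event recorded.

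A 28-fold difference in tablets and a 7-fold difference in days leave no trace.

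**4. Arms start alike, then differ.** The documents give no usage rates, so all rates here are assumed. Set-up: 2,000 trials, 150 per arm; the same share of users in both arms; first use on Day 1, 2 or 3 with probability 0.7, 0.2, 0.1 in both arms; days of use geometric and cut at Day 7; 1 to 3 tablets per day of use; non-users censored at day 8. Entries are the share of trials with p < 0.05 at 40%, 60% and 80% users.

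| Mean days of use | Log-rank, first use | Rank-sum, total tablets |
|---|---|---|
| 3 vs 2 | 5.0%, 5.8%, 5.1% | 9.5%, 26.1%, 62.8% |
| 4 vs 2 | 5.6%, 4.7%, 6.4% | 18.0%, 57.3%, 95.1% |

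The log-rank rate sits near 5% by construction, because first use has the same distribution in both arms. That is the point: such a difference is invisible to it.

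**5. A second set of assumptions, including a case that favours the SAP.** 2,000 trials, 150 per arm, totals over Days 1 to 4, unstratified tests.

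| Scenario | Log-rank | Tablets | Days |
|---|---|---|---|
| 30% users in both arms, heavier continued use in one | 4.3% | 35.0% | 25.3% |
| 50% users in both arms, same contrast (mean 0.9 vs 3.6 tablets) | 5.1% | 96.6% | 88.5% |
| 70% users in both arms, same contrast | 5.8% | 100% | 100% |
| 30% vs 50% ever use, same intensity among users | 94.4% | 91.6% | 92.1% |
| No difference | 4.5% | 4.7% | 4.4% |

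When the arms differ in who starts, the log-rank test does as well as the other two.

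**6. Behaviour of the Hodges-Lehmann estimate.** It is the median of all test-minus-control differences. A positive difference needs a test-arm user and a negative one a control-arm user. With 40% users per arm, at most 40% of differences are positive and at most 40% negative, so the estimate is exactly 0 whatever the amounts. With 60% users, 0.6 × 0.4 = 24% of pairs are positive because only the test subject used rescue. To move the estimate off 0, the test subject must exceed the control in (0.50 − 0.24)/0.36 = 72% of user-user pairs. Under the assumptions of step 4 (500 trials per setting, unstratified), the estimate was 0 in all trials at 40% users. At 60% users it was 0 in 81–96% of trials for tablets and 90–99% for days.

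**The case against.** **The substitute is not blind to rescue use, and description remains.** This stands. Step 5 shows that it detects differences in who starts, and a shift in start day would also show in the Kaplan-Meier curves. SAP 4.4.3 keeps a summary of tablets, date, time and reason. Output references are blacked out and the display list is not reproduced, so whether a table also counts days or splits tablets by reason cannot be judged. The text promises neither.

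**The change is declared.** This stands too: it is in section 5 with a reason, so it is not a concealed switch. The reason does not cover what was lost.

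**The protocol's estimate is weak.** Partly right. Step 6 shows that Hodges-Lehmann is often 0. But the rank test still responds to amount, and a difference in means would complement it. The same threshold also limits the SAP method: if fewer than half of an arm ever uses rescue and few are censored early, median time to first use is not reached.

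**Restoring the protocol totals would not isolate use before Day 5.** Correct. They run over the whole study and include tablets after Visit 3, so a separate total to Visit 3 is needed.

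**A stronger reading is tempting: that hidden rescue imbalance biases the Day 5 result toward non-inferiority.** Illustrative figures can be produced. With SE = 22 × √(2/120) = 2.840 and 238 degrees of freedom, suppose paracetamol before the reading is 2, 5 or 10 percentage points more frequent in the test arm and lowers POM by 5 to 20 mm. The false non-inferiority rate at a true 13 mm difference then moves from 2.5% to 2.7–3.4%, 3.1–5.4% or 3.7–10.4%. The documents do not support this as a finding. They give no usage rate and no effect of paracetamol on POM. The top of the assumed effect range exceeds the 13 mm margin. Rescue is also barred for 12 hours before Visit 3, three times the 4-hour minimum interval between doses. Nor does the entry criterion of POM at least 50 mm show that most subjects would take a tablet on Day 1, since POM is pain under the investigator's manipulation.

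**Conclusion.** The point holds as a gap between endpoint and analysis. Two retained secondary endpoints lose all 4 of the protocol's between-arm comparisons in the SAP text. Their replacement measures neither, ignores everything after the first tablet, is not split by reason, and cannot show unequal amount or duration among subjects who start alike.

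The identity of the 1-tablet and 28-tablet cases follows from the documents alone. The rejection rates rest on assumed usage patterns. They show what each method can and cannot see, not which pattern is likely. The Day 5 figures are illustrations, not evidence of bias. Study success rests on the primary endpoint, which is untouched. This is worth correcting before unblinding because it is cheap and affects how the primary result will be read; it does not threaten the primary analysis.

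**What to change.** In SAP 4.4.3, before unblinding:

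1. Restore the Protocol 12.2.6 comparison: total tablets and days of use, for ankle pain (by RMREAS) and overall, by CMH with modridit scores stratified by center, with the Hodges-Lehmann difference and 95% CI, on mITT and PP.
2. Add the difference in mean tablets and mean days with 95% CI, since the Hodges-Lehmann estimate will often be 0 if many subjects use none.
3. Add the same totals from first dose to Visit 3, by arm, to support reading of the Day 5 POM. Under the step 4 assumptions with 4 versus 2 days, a test on such a tablet total detected the difference in 14%, 48% and 89% of 1,000 trials at 40%, 60% and 80% users.
4. Keep time to first use as an addition.

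The cost is SAP text and one extra table. Tablets, date, time and reason are already on the Rescue Medication CRF page. Cutting the total exactly at Visit 3 also needs that visit's clock time, assumed to be recorded. SAP 2.2 places finalization of the plan before unblinding, and the available version is labelled draft. The primary analysis and sample size do not change. The SAP 4.2.2 reference to Appendix 4 for prohibited medication, which is in Appendix 5, is a separate clerical correction.
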